6.4. Vital Signs

Vital signs (including temperature, pulse rate, systolic blood pressure, diastolic blood pressure, and respiratory rate) will be collected throughout the study. Pulse rate and respiratory rate are optional.

Vital signs results will be classified into 4 or 5 categories (low, borderline low, normal, borderline high, or high) according to Table 4 below. Shift tables based on this classification will be summarized from baseline to the last post-baseline visit value.

Vital Sign	Low	Borderline Low	Normal	Borderline High	High
Heart Rate (beats per minute)	< 50	50-59	60-90	91-99	≥100
Systolic BP (mmHg)	< 80	-	80-120	121-139	≥140
Diastolic BP (mmHg)	< 60	-	60-80	81-89	≥90
Respiratory Rate (breaths per minute)	< 12	-	12-20	21-24	≥25
Temperature (°C)	< 35.0	35.0-36.4	36.5-37.2	37.3-37.9	≥ 38.0

Table 4:Classification of Vital Signs

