- ^f ECOG, PE, pregnancy test for WCBP, and hematology and chemistry labs (if all parameters are within normal range) do not need to be repeated at C1D1 if performed within the previous 4 days during Screening.
- ^g Vital signs (BP and body temperature) will be measured before start of infusion; post infusion vital signs should be collected as clinically indicated for potential infusion-related reaction.
- ^h Hematology and chemistry labs may be performed up to 4 days prior to D1 of each cycle, and as clinically indicated while on treatment, with results reviewed before each MIRV administration. In the event of severe toxicity, laboratory tests must be repeated as clinically necessary until the toxicity resolves or stabilizes to baseline level.
- ⁱ For women of childbearing potential (WCBP), a urine or serum pregnancy test must be performed within the 4 days prior to D1 of each cycle, and at the 30-Day Follow-up visit. It is recommended to perform monthly pregnancy tests for 3 months after the last dose of MIRV. Additional testing may be performed in accordance with institutional requirements or local regulation.
- ^j Baseline ophthalmic exams will be performed by an ophthalmologist within 14 days before C1D1 and will include the following: visual acuity (with/without corrective lens; whichever best reflects the patient's usual functioning), slit lamp examination, intraocular pressure measurement, and indirect fundoscopy. All patients who have an ophthalmic exam on study treatment (post-baseline) due to emergence of visual signs or symptoms will have a complete ophthalmological examination performed at EOT visit or 30-Day Follow-up visit.
- ^k Ocular symptoms assessment will be performed by the treating physician or other qualified individual before the start of each cycle. For patients reporting > CTCAE Grade 1 ocular symptoms, treatment will be held until the patient is evaluated by an ophthalmologist for a complete examination.
- ^l Radiologic tumor assessment by CT/MRI scan. The same method of radiographic assessment used at Screening must be used at all subsequent radiographic assessments.

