The MIRV safety profile was predominantly characterized by low-grade nausea (51%), diarrhea (40%), and blurred vision (40%). These TEAEs are generally managed and mitigated with antiemetics, antidiarrheals, and lubricating/steroid eye drops. In the MIRV group, there were fewer \geq Grade 3 TEAEs, and fewer TEAEs leading to dose reduction or delay and treatment discontinuation (46%, 37%, and 12%, respectively) compared with the IC chemotherapy group (61%, 45%, and 19%, respectively). While myelosuppression is an important safety issue with PLD and Topo, MIRV is associated with less myelosuppression compared to IC chemotherapy, with lower rates of neutropenia (7% vs. 39% all grade; 0% vs. 21% Grade 3+), thrombocytopenia (11% vs. 16% all grade; 0% vs. 4% Grade 3+) and anemia (14% vs. 29% all grade; 2% vs. 11% Grade 3+). Similarly, neurotoxicity is an important safety issue with Pac; MIRV, an ADC with the tubulin-directed payload DM4, is associated with less peripheral neuropathy than Pac (15% vs. 28% Grade 2+) and less alopecia (3% vs. 22% all grades). The safety profile of MIRV in the high FR α subset is consistent with that observed in the overall MIRV safety population.

For MIRV the mean half-life ($t_{1/2}$) was 115.1 hour (4.8 days), with little evidence of accumulation (mean accumulation ratio of 1.102).

There was no apparent relationship between patients testing positive for anti-drug antibodies (ADA) and MIRV exposure.

Please see the [Investigator Brochure](#) for information on Study IMGN853-0403.

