9.2. End of Treatment Visit

Patients may voluntarily withdraw from the study drug at any time for any reason, and without prejudice to further treatment. In addition, patients may be withdrawn by the Investigator if they do not feel the patient is deriving clinical benefit or because the patient is experiencing unacceptable toxicity. The reasons for which a patient may be prematurely discontinued are listed in [Section 5.6](#). The clinical trial database will capture reasons for withdrawal.

Patients who withdraw or are removed from the study treatment will have an EOT visit within 7 days of the decision to discontinue study drug. Patients will undergo assessments as outlined in [Table 2](#).

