9.3. Follow-up Assessments

9.3.1. 30-Day Follow-up Visit

A 30-Day Follow-up visit will occur 30 days (+14 days) after last dose of MIRV and should occur prior to the start of new anticancer therapy.

In some cases, nonserious AE observations may continue beyond the safety visit. All ocular AEs will be followed until resolution, stabilization, or return to baseline. In these instances, additional information may be requested by ImmunoGen to adequately categorize the nature of the toxicity.

All SAEs will be followed until they resolve, stabilize or return to baseline, regardless of time from last dose or last visit.

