6.3. Clinical Laboratory Results

Laboratory test results (including hematology, coagulation, serum chemistry, and urinalysis) and abnormal laboratory values will be presented in data listings.

CTCAE Version 5.0 laboratory grades will also be presented. CTCAE grades will be derived based on laboratory results and will not factor in clinical evaluations.

Shift tables summarizing the changes from baseline in severity of laboratory grades will be provided for laboratory parameters graded according to CTCAE Version 5.0. Grade 3 or higher laboratory values will be summarized based on the worst grade observed during MIRV treatment or within 30 days of last dose.

Clinically significant values in liver function tests (LFTs) will be summarized by the following categories, using the maximum value while on MIRV. The denominator for the summaries will be the number of patients who had at least 1 non-missing value during treatment. The categories for each test are not mutually exclusive:

- Aspartate aminotransferase (AST)
 - $> 3 \times ULN$
 - $> 5 \times ULN$
 - $> 10 \times ULN$
 - $> 20 \times ULN$

- Alanine Aminotransferase (ALT)
 - $> 3 \times ULN$
 - $> 5 \times ULN$
 - $> 10 \times ULN$
 - $> 20 \times ULN$
- AST or ALT
 - $> 3 \times ULN$
 - $> 5 \times ULN$
 - $> 10 \times ULN$
 - $> 20 \times ULN$
- Total bilirubin (TBILI)
 - >ULN
 - $> 2 \times ULN$
- Alkaline phosphatase (ALP)
 - > 1.5 × ULN
- (AST or ALT) and TBILI (concurrent)
 - AST or ALT > $3 \times$ ULN and TBILI > $1.5 \times$ ULN
 - AST or ALT > $3 \times$ ULN and TBILI > $2 \times$ ULN
- (AST or ALT) and ALP and TBILI (concurrent)
 - AST or ALT > 3 × ULN and ALP < 2 × ULN and TBILI > 2 × ULN

Here, concurrent means that all the associated LFTs must be from the same visit. In addition, worst postbaseline grade for LFTs will be summarized. Because baseline values of LFTs are already taken into account in CTCAE V5.0, shift table from baseline to worst postbaseline grade will not be generated for LFTs.

Results from pregnancy tests will be provided in listings.

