6.7. Concomitant Procedures

All procedures within 4 weeks of Cycle 1 Day 1 and through 30 days after last study treatment must be recorded on the appropriate CRF.

Prior procedures are defined as occurring before the first dose of MIRV (by procedure date).

Concomitant procedures are defined as procedures with a procedure date on or after the first dose of MIRV, and within 30 days of the last dose of MIRV, as follows:

• Procedures are defined as concomitant procedures with a procedure date on or after the first dose of MIRV, and within 30 days of the last dose of MIRV or prior to the start of a new anti-cancer treatment, whichever occurs first.

Prior and concomitant procedures will be coded using MedDRA (Version 24.0), associating lower-level terms with PT and SOC by the primary hierarchy. Summary tables will be provided for prior and concomitant procedures. The tables will display number and percentage of patients who reported at least 1 procedure in each SOC represented in the CRF data. Within each SOC, the tables will display number and percentage of patients reporting at least 1 concomitant procedure as designated by PT.

A complete listing of procedures will be generated. The listing will indicate which procedures are prior and which are concomitant. The listing will display entries from the concomitant procedures form, ordered within patient by date of procedure. The listing will display the recorded term from the CRF and the SOC and PT.

6.8. **Ophthalmic Examinations**

Ophthalmic Examinations are collected at the Screening, End-of-Treatment, and 30-Day Followup Visits. Results of the ophthalmic examinations will be presented in data listings.

Worst decline in both eye best corrected visual acuity (BCVA) grade will be summarized. Shift of both eye BCVA from baseline to worst post baseline will be summarized using the following categories: $\geq 20/40$, < 20/40 to $\geq 20/200$, and < 20/200.

Shift of intraocular pressure (mmHg) from baseline to highest post baseline value will be summarized using the following categories: ≤ 22 and ≥ 22 .

Cataract shift from baseline to maximum on treatment CTCAE grade will be summarized based on data collected on the ocular symptom assessments CRF.

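### The only vital-sign table planned in the SAP runs to the last visit, so an on-treatment abnormality that resolves before then does not appear in it

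*SAP*

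**What the plan says.** SAP 6.4 sorts each vital sign into four or five categories from low to high (SAP Table 4) and plans a single tabulation: "Shift tables based on this classification will be summarized from baseline to the last post-baseline visit value". It sets no time limit on that last value and plans no worst-value, by-visit or change-from-baseline summary.

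Elsewhere the SAP looks across the treatment period. In SAP 6.3, Grade 3 or higher laboratory values are "summarized based on the worst grade observed during MIRV treatment or within 30 days of last dose", and liver function tests use the maximum on MIRV. In SAP 6.8, "Shift of both eye BCVA from baseline to worst post baseline will be summarized using the following categories" and "Shift of intraocular pressure (mmHg) from baseline to highest post baseline value will be summarized"; cataract uses the maximum on-treatment grade.

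Protocol Table 2 schedules vital signs at Screening, on Day 1 of every cycle, at EOT and at the 30-Day Follow-up, and not during survival follow-up. On dosing days, "Vital signs (BP and body temperature) will be measured before start of infusion"; a post-infusion reading is taken only when there is a clinical reason to suspect an infusion-related reaction. Patients who stop "will have an EOT visit within 7 days of the decision to discontinue study drug", and "A 30-Day Follow-up visit will occur 30 days (+14 days) after last dose of MIRV".

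Protocol 10.3 promises a per-patient listing of vital signs at each assessment and a summary of their changes from baseline. SAP 6.4 repeats neither.

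**The concern.** Vital signs are part of an additional secondary endpoint (Protocol 2.2.3), and Protocol 5.5.5 names fever, hypotension and palpitations among the signs of infusion-related reactions. A table that reads only each patient's last value cannot show an event of that kind once the patient has recovered and attended a later visit. The SAP gives no reason for treating vital signs differently from the eye measurements and liver tests. At stake is how informative one descriptive safety table is. No decision rule depends on it.

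**Working it through.** The plan states no figure on this point, so there is none to reproduce. The check traces the rule through the visit schedule.

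**1. Which reading is last.** After MIRV stops, the remaining scheduled readings are EOT and the 30-Day visit. The table takes the 30-Day value, or the EOT value if the 30-Day visit is missed. A patient still on MIRV at the data cutoff contributes a pre-dose on-treatment value.

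**2. How many readings are used.** SAP 3.2 defines baseline as the last value on or before the day of first dose, so Cycle 1 Day 1 is not post-baseline. With six cycles: Cycles 2 to 6 give 5 readings, EOT 1 and 30-Day 1, so 5 + 1 + 1 = 7. The table uses 1 of 7, or 14%.

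**3. Match with the safety window.** The 30-Day visit falls between day 30 and day 30 + 14 = 44 after the last dose. Treatment-emergent events end at 30 days after the last dose, or earlier if new anticancer therapy starts (SAP 6.2). A reading on days 31 to 44 is therefore outside that window but is still the one tabulated.

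**4. Rules side by side.**

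| Measure | Post-baseline value summarised |
|---|---|
| Vital signs (SAP 6.4) | last |
| Visual acuity (SAP 6.8) | worst |
| Intraocular pressure (SAP 6.8) | highest |
| Cataract grade (SAP 6.8) | maximum on treatment |
| Liver function tests (SAP 6.3) | maximum on MIRV |
| Grade 3 or higher laboratory values (SAP 6.3) | worst, to 30 days after last dose |
| General laboratory shift tables (SAP 6.3) | not stated |

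For the last row, a worst-grade endpoint is only implied, by the remark that no such shift table will be made for liver tests.

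**5. Illustration of size.** The documents give no rate of vital-sign abnormality, so p and k are assumptions. Let each of k post-baseline readings be abnormal independently with probability p. A last-value table then shows p of patients as shifted; a worst-value table shows 1 − (1 − p)^k.

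| p (last-value table) | k = 4 | k = 6 | k = 8 | k = 10 |
|---|---|---|---|---|
| 2% | 7.8% | 11.4% | 14.9% | 18.3% |
| 5% | 18.5% | 26.5% | 33.7% | 40.1% |
| 10% | 34.4% | 46.9% | 57.0% | 65.1% |

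This can be read two ways. It shows how much a last-value table leaves out. Because p is the same on and off drug here, it also shows how far a worst-value table rises with no drug effect at all. At the other extreme, if abnormalities occurred only on drug and had all cleared by the last visit, the last-value table would show none of them.

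**6. Residual drug.** Protocol 1.6.2 reports that the mean half-life "was 115.1 hour (4.8 days), with little evidence of accumulation" (115.1/24 = 4.80 days). Assuming single-phase decay, the fraction left is 0.5^(hours/115.1): 4.8% at day 21, 1.3% at day 30 and 0.2% at day 44. Day 21 is the next scheduled pre-dose reading, so the routine on-treatment readings are themselves troughs. Exposure at the last visit is lower, but the contrast is small, and nothing in the documents ties vital signs to residual concentration. The argument does not rest on this.

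**The case against.** The strongest reply is that clinically important events are caught elsewhere. Clinically significant vital-sign abnormalities are adverse events (Protocol 8.1.1.1). They reach the treatment-emergent and Grade 3 or higher tables (SAP 6.2), and the hypersensitivity query tables address infusion-related reactions (SAP 6.2.2). Protocol 10.3 adds the per-assessment listing. This stands, and it limits the point to one table. It does not remove it: adverse event capture depends on a judgement of clinical significance, whereas SAP Table 4 applies fixed cut-offs such as systolic pressure of 140 mmHg or more, and a listing is not a summary.

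A second reply is that taking the extreme of several readings against one baseline inflates shifts, particularly with narrow bands such as systolic 121–139 mmHg, and a single-arm trial has no control to calibrate against. This also stands. It is a reason to keep the last-value table alongside and to label the new one plainly.

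A reader might go further and infer that on-treatment abnormalities vanish from the safety report, or that the tabulated reading is always drug-free. The documents support neither. Persistent abnormalities still show, patients on MIRV at the cutoff contribute on-treatment values, and EOT is timed from the decision to stop, so it need not be remote from the last dose. A reader might also infer that every laboratory shift in the SAP uses the worst value; SAP 6.3 does not state that.

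**Conclusion.** The point holds in a limited form. Followed as written, SAP 6.4 leaves out of its only vital-sign table any on-treatment abnormality that resolved before the patient's last reading. For patients who have stopped MIRV, that reading is normally EOT or the 30-Day visit and may fall after the treatment-emergent window closes. This differs from how the SAP handles the eye measurements, liver tests and Grade 3 or higher laboratory values, and no reason is given.

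The number of hidden shifts cannot be estimated from the documents; the percentages above depend on assumed p, assumed k and independence between visits. The conclusion assumes that patients attend the scheduled visits. It is a minor weakness in safety reporting, with no effect on response rate, duration of response or any test.

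**What to change.** In SAP 6.4:

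- Add shift tables from baseline to the lowest value and, separately, to the highest value from first dose through 30 days after last dose. Two tables are needed because the categories run in both directions. The window matches the Grade 3 or higher laboratory summary.
- State that unscheduled and post-infusion readings count. SAP 3.4 takes the first non-missing value at a visit unless several are expected, and post-infusion readings are taken only when clinically prompted. Without this statement they could be dropped, and the new tables would rest mainly on pre-infusion values.
- Keep the last-value table as secondary.
- Show denominators for pulse and respiratory rate, which are optional in SAP 6.4 and absent from the protocol's vital signs.
- Carry over the change-from-baseline summary promised in Protocol 10.3.

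The cost is a small reprogramming task on data already collected, and SAP 1.1 allows changes before final database lock. The downside is that more shifts will appear, partly by chance; a footnote should say that the extreme of several readings is being compared with a single baseline.

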6.5. ECGs

ECGs are collected at screening visit only. All ECG results will be presented in data listings. If a different correction for QT is captured in the CRF, that QTc will be reported in the listing for that patient with QTcF.

6.6. Concomitant Medications

All medications and supportive therapy taken within 4 weeks prior to Cycle 1 Day 1 and through 30 days after last study treatment must be recorded on the appropriate CRF. The identity of all medications, dosage, route of administration, frequency, duration of administration, and indication for use will be recorded in the appropriate sections of the CRF.

Prior medications are defined as medications with a stop date prior to the first dose of MIRV.

Concomitant medications are defined as medications which are taken during the course of study treatment and within 30 days of the last dose of MIRV, as follows:

- Medications started before the first dose of MIRV, but with a stop date after the first dose of MIRV and within 30 days of the last dose of MIRV will be considered concomitant medications.
- Medications started before the first dose of MIRV that are ongoing will be considered concomitant medications.
- Medications started after the first dose of MIRV and within 30 days of the last dose of MIRV or before the start of a new anti-cancer treatment, whichever occurs first, are considered concomitant medications.
- Medications started before the first dose of MIRV, but with a stop date after the first dose of MIRV and within 30 days of the last dose of MIRV or prior to the start of a new anti-cancer treatment, whichever occurs first, will be considered concomitant medications.

Prior and concomitant medications will be coded using the March 2021 version of World Health Organization drug dictionary (WHO Drug). Summary tables will be provided for prior and concomitant medications.

Summary tables will be organized to display the anatomical main class of each coded medication (ATC Level 1 term) and, within that, the pharmacological subgroup (ATC Level 3 term) of the coded medication. The summary table will display number and percentage of patients who reported using at least 1 medication in each represented pharmacological subgroup. If a patient has more than 1 medication in the subgroup, the patient will be counted only once.

A complete listing of medications will be generated by patient. The listing will indicate which medications are prior and which are concomitant. The listing will display entries from the concomitant medications form, ordered within patient by start date. The listing will display the recorded term from the CRF and the WHO Drug anatomical main class (ATC Level 1 term) and pharmacological subgroup (ATC Level 3 term).

6.7. Concomitant Procedures

All procedures within 4 weeks of Cycle 1 Day 1 and through 30 days after last study treatment must be recorded on the appropriate CRF.

Prior procedures are defined as occurring before the first dose of MIRV (by procedure date).

Concomitant procedures are defined as procedures with a procedure date on or after the first dose of MIRV, and within 30 days of the last dose of MIRV, as follows:

• Procedures are defined as concomitant procedures with a procedure date on or after the first dose of MIRV, and within 30 days of the last dose of MIRV or prior to the start of a new anti-cancer treatment, whichever occurs first.

Prior and concomitant procedures will be coded using MedDRA (Version 24.0), associating lower-level terms with PT and SOC by the primary hierarchy. Summary tables will be provided for prior and concomitant procedures. The tables will display number and percentage of patients who reported at least 1 procedure in each SOC represented in the CRF data. Within each SOC, the tables will display number and percentage of patients reporting at least 1 concomitant procedure as designated by PT.

A complete listing of procedures will be generated. The listing will indicate which procedures are prior and which are concomitant. The listing will display entries from the concomitant procedures form, ordered within patient by date of procedure. The listing will display the recorded term from the CRF and the SOC and PT.

6.8. **Ophthalmic Examinations**

Ophthalmic Examinations are collected at the Screening, End-of-Treatment, and 30-Day Followup Visits. Results of the ophthalmic examinations will be presented in data listings.

Worst decline in both eye best corrected visual acuity (BCVA) grade will be summarized. Shift of both eye BCVA from baseline to worst post baseline will be summarized using the following categories: $\geq 20/40$, < 20/40 to $\geq 20/200$, and < 20/200.

Shift of intraocular pressure (mmHg) from baseline to highest post baseline value will be summarized using the following categories: ≤ 22 and ≥ 22 .

Cataract shift from baseline to maximum on treatment CTCAE grade will be summarized based on data collected on the ocular symptom assessments CRF.

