5.5.2. Ocular Disorders

Changes in visual acuity resulting from reversible keratopathy have been reported in other studies of DM4-containing immunoconjugates that use the SPDB linker ([Younes 2012](#)). Patients receiving MIRV in the Phase 1 and 3 trials (IMGN853-0401, IMGN853-0403) reported ocular AEs consistent with reversible keratopathy/corneal epitheliopathy.

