7.9.2. Ophthalmic Examination

An ophthalmic examination will be performed at Screening (within 14 days prior to first dose of study drug) by an ophthalmologist and will include the following: distant visual acuity, best corrected visual acuity, slit lamp examination, intraocular pressure measurement, and indirect funduscopy. Patients who experience ocular TEAEs while on study will have a complete ophthalmologic exam performed at the emergence of the symptoms and at every other cycle thereafter. All patients who have an ophthalmic exam on study treatment (post-baseline) will have a complete ophthalmologic exam performed at the EOT visit or 30-Day Follow-up visit ([Table 2](#)).

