6.9. Ocular Symptom Assessments

Results of the ocular assessments will be presented in data listings.

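### The vision shift table in SAP 6.8 uses three wide acuity bands of an undefined both-eye BCVA, so a three-line loss from 20/20 shows as no change

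*SAP*

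**What the plan says.** SAP 6.8 (Ophthalmic Examinations) opens with a general rule: "Results of the ophthalmic examinations will be presented in data listings". It then plans four summaries. Two concern acuity:

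- "Worst decline in both eye best corrected visual acuity (BCVA) grade will be summarized". No grading scale is given.
- "Shift of both eye BCVA from baseline to worst post baseline will be summarized using the following categories": 20/40 or better; worse than 20/40 down to and including 20/200; worse than 20/200.

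The other two are an intraocular pressure shift and a cataract shift. No summary of slit-lamp findings is planned. For ocular symptoms, SAP 6.9 says: "Results of the ocular assessments will be presented in data listings".

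Protocol 7.9.2 specifies the Screening exam as "distant visual acuity, best corrected visual acuity, slit lamp examination, intraocular pressure measurement, and indirect funduscopy". Patients with an ocular treatment-emergent event then have a complete exam when symptoms emerge and every other cycle after that. Protocol 5.5.2 says that patients in the Phase 1 and Phase 3 trials "reported ocular AEs consistent with reversible keratopathy/corneal epitheliopathy".

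SAP 6.2 makes ocular events a focused safety group, tabulated by preferred term and maximum CTCAE grade, from a sponsor list of terms to be fixed before final database lock.

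**The concern.** Ocular toxicity is this drug's characteristic harm. Protocol 1.6.2 reports blurred vision in 40% of MIRV patients in the earlier Phase 3 trial, within a mainly low-grade profile. As an illustration, the same rate among about 110 patients would be 0.40 × 110 = 44 patients. For them a reader will want to know how much acuity was lost at worst.

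A shift table with two cut points answers a different question: whether a patient crossed 20/40 or 20/200. With bands this wide, a larger loss can go uncounted while a smaller one is counted, depending only on where the patient started. The other acuity summary might compensate, but its scale is not stated. Both summaries also rest on a *both eye* measure that the SAP does not define, so two programmers could produce different tables from the same data.

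**Working it through.** The documents give no figure for acuity lost, so there is no plan figure to reproduce. The check applies the SAP's cut points to a chart.

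**Inputs.** Cut points 20/40 and 20/200 (SAP 6.8). The chart is an assumption, because the documents name none: 0.1 logMAR per line, with denominators 10, 12.5, 16, 20, 25, 32, 40, 50, 63, 80, 100, 125, 160, 200, 250, 320, 400.

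**Formula.** logMAR = log10(denominator / 20). Loss = log10(later denominator / baseline denominator), and lines lost = loss / 0.1.

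| Change | Loss (logMAR) | Lines | Shift table shows |
|---|---|---|---|
| 20/20 to 20/40 | log10(40/20) = 0.301 | 3 | no shift |
| 20/50 to 20/200 | log10(200/50) = 0.602 | 6 | no shift |
| 20/40 to 20/50 | log10(50/40) = 0.097 | 1 | shift |

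**Largest loss that stays in the starting band, in lines.**

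- Top band: 6 from 20/10, 5 from 20/12.5, 4 from 20/16, 3 from 20/20, 2 from 20/25, 1 from 20/32, 0 from 20/40.
- Middle band: 6 from 20/50, 5 from 20/63, 4 from 20/80, 3 from 20/100, 2 from 20/125, 1 from 20/160, 0 from 20/200.
- Bottom band: no lower limit.

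**Count over the 12 levels from 20/16 to 20/200.**

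- A three-line loss is hidden from 20/16, 20/20, 20/50, 20/63, 20/80 and 20/100: 6 of 12.
- A two-line loss is hidden from those six plus 20/25 and 20/125: 8 of 12.

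These are counts of chart levels, not of patients.

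**Sensitivity to the chart.** On a traditional chart (20/20, 25, 30, 40, 50, 70, 100, 200), 20/20 to 20/40 is still three lines. The step from 20/50 to 20/200 becomes three printed lines, although the loss is still 0.602 logMAR. The three-line result from 20/20 therefore does not depend on the chart. The six-line label does.

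**Readings of *both eye*.**

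- Binocular acuity (taken to follow the better eye), better-eye acuity, or a rule that both eyes must decline: a loss confined to one eye shows no shift.
- Each eye tabulated, or the worse eye used: a one-eye loss is not hidden for this reason.

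**What the adverse event tables add.** Protocol 8.1.1.1 counts physical signs as possible adverse events, so keratopathy seen at an exam can be reported and would be tabulated if its term is on the sponsor's list. The same section counts an abnormal test result as an event only under conditions, such as causing signs or symptoms or being clinically significant. An exam finding can therefore remain outside these tables, and a preferred term with a grade does not state lines lost.

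**The case against.** The strongest reply is that SAP 6.8 plans two acuity summaries and the band shift is only one. CTCAE v5.0 grades are used for adverse events and laboratory values elsewhere in the SAP, and a CTCAE grade is used for cataract in the same section. A CTCAE reading of the BCVA grade is therefore plausible, and it might show losses that the bands miss. This stands in part. The documents do not show that the grade summary misses these losses, nor that it catches them, because the scale is not stated.

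A reader might infer that losses of six lines would routinely go unseen. That is not supported. Six lines needs a baseline such as 20/50 (or 20/10) on a 0.1 logMAR chart; from 20/20 the limit is three. No baseline acuity distribution is given. Exclusion criterion 6 removes corneal disorders and several active eye conditions, although it sets no minimum acuity, so the share of patients affected is unknown.

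A reader might also infer that one-eye losses are hidden, or that corneal toxicity reaches no table. The first holds only under some readings of an undefined term. The second is wrong: ocular events are tabulated by term and grade, with relatedness, dose changes and time to onset. Only slit-lamp findings as examined are left to listings.

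Finally, no test, sample size or primary estimate depends on this table, and individual exam results are listed. That limits the severity but does not make the table informative.

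**Conclusion.** The point holds in this limited form. The band shift is a coarse summary that can miss a three-line loss from 20/20 and, on a 0.1 logMAR chart, a six-line loss from 20/50, while counting a one-line loss from 20/40. *Both eye* and *BCVA grade* are undefined, so it cannot be said whether one-eye losses are visible or whether the grade summary fills the gap. The ocular event tables are useful but do not measure acuity lost.

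The line counts rest on the assumed chart. The number of patients affected cannot be estimated from the documents, and they do not establish that the trial's vision results would be understated overall. The ORR analysis and the other efficacy results are unaffected. This is a low-cost improvement to the reporting of the drug's characteristic harm. The slit-lamp part is secondary, because the case report form is not shown.

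**What to change.** In SAP 6.8:

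1. State that BCVA is analysed for each eye and for the worse-affected eye, meaning the eye with the larger loss from its own baseline. Define the BCVA grade by naming its scale.
2. Convert BCVA to logMAR and report the number and percentage of patients whose worst post-baseline loss from baseline is at least 2, at least 3 and at least 6 lines. These thresholds are a proposal, not taken from the documents.
3. Use all post-baseline exams, including those done during treatment after an ocular event. SAP 6.8 describes exams as collected at Screening, End of Treatment and the 30-Day Follow-up, whereas Protocol 7.9.2 also requires on-treatment exams after ocular events. A reversible low point could be missed if those are left out.
4. Keep the three-band shift as a secondary display.
5. Where the case report form records slit-lamp corneal findings in codable form, add a present/absent shift from baseline to worst post-baseline.

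SAP 1.1 allows changes before final database lock. The cost is SAP wording and a small amount of programming. No exam is added and clinical management does not change. Before finalising, confirm that acuity is recorded per eye in a form that can be converted to logMAR.
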